10. DISCONTINUATION OF STUDY TREATMENT AND WITHDRAWAL OF SUBJECTS FROM THE STUDY

10.1. Discontinuation of Study Treatment

A subject must permanently discontinue study treatment for any of the following reasons:

- The subject becomes pregnant. Study treatment must be discontinued immediately, and the pregnancy must be reported according to the instructions in Section [15.4.1](#).
- Any seizure event. If a seizure event is suspected, the subject must discontinue study treatment and be referred to a neurologist for appropriate follow-up (see Section [7.3](#)). An effort should be made to collect a [REDACTED] as soon as possible after the event.
- The subject withdraws consent.
- The subject experiences a medical emergency that necessitates permanent discontinuation of study treatment or unblinding of the subject's treatment assignment.
- The subject experiences an AE requiring continued treatment that meets exclusionary criteria.
- The subject has confirmed ALT or AST $>5 \times$ ULN, or confirmed ALT or AST $>3 \times$ ULN and bilirubin $>2 \times$ ULN.
- Depending on the specifics of the subject's C-SSRS as assessed by the Investigator, subjects must have their suicidality managed appropriately by clinicians and must discontinue from the treatment.
- At the discretion of the Investigator, for medical reasons.
- At the discretion of the Investigator or the Sponsor, for noncompliance with the terms of the protocol.
- The primary reason for discontinuation of study treatment must be recorded in the subject's case report form (CRF).

All subjects who discontinue study treatment prematurely will be asked to remain in the study and continue all protocol-specified visits and procedures. At a minimum, these visits should include assessment of AEs/SAEs and concomitant medications and key clinical assessments. Subjects who discontinue study treatment prematurely will also be asked to return to the study site for an SFU Visit 14 days after receiving the last dose of study treatment.

CONFIDENTIAL

The information contained herein may not be used, disclosed, or published without the written consent of Biogen MA Inc.

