The change from baseline will be summarized by treatment group at each post-baseline visit. A mixed model repeated measures (MMRM) model will be used as the primary analysis to analyze change from baseline of the endpoint of interest, using fixed effects of treatment group, study visit, study visit-by-treatment interaction, baseline value of the endpoint, and baseline-by-visit interaction. Region (stratification factor for randomization) will be included as a fixed effect but may be omitted in the case that the model fails to converge. An unstructured covariance matrix will be used to model the within-patient variance-covariance errors. If the unstructured covariance matrix results in a lack of convergence, the following structures will be used in order: heterogeneous Toeplitz (TOEPH), heterogeneous compound symmetry (CSH), antedependence (ANTE1), heterogeneous autoregressive (ARH1), autoregressive (AR1) and compound symmetry (CS). The first covariance structure yielding convergence will be used. If a structured covariance is used, the empirical “sandwich” estimator of the standard error (SE) of the fixed effects parameters will be used to deal with possible model misspecification of the covariance matrix. The Kenward-Roger approximation will be used to estimate the denominator degrees of freedom. The primary treatment comparison is BIIB104 treatment group versus placebo at the end of Week 12. In the primary analysis, missing data are assumed to be missing at random (MAR) [Rubin 1976]. To account for the interim analysis at the time of the final analysis, the median unbiased estimate of the primary treatment effect will be calculated as a supporting analysis.

However, for UPSA-Bi and SCoRS, which only have assessments at baseline and at Week 12, the primary analysis will be based on subjects who have both baseline and Week 12 assessments. An analysis of covariance (ANCOVA) model will be applied adjusting for treatment group and baseline value of the endpoint (UPSA-Bi or SCoRS, respectively).

Sensitivity analysis: Reference-based multiple imputation approach

The following sensitivity analysis will be performed to assess the robustness of the primary analysis with respect to deviation from the MAR assumption. All sensitivity analyses will be conducted for the ITT population.

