Intermittent (non-monotonic) missing data will be imputed based on the MAR assumption and with a multiple imputation model using Markov chain Monte Carlo (MCMC) method within each treatment group. The imputation models will include baseline value and the values at each post-baseline week for the endpoint of interest. The MCMC method in the PROC MI procedure in SAS will be used with a single chain, with a burn-in of 1000, and a thinning of 100 and non-informative priors for all parameters.

Reference-based multiple imputation (MI) approach will be used to impute missingness post treatment discontinuation and consider a missing not at random (MNAR) mechanism for monotonic missing data. Imputed values in the reference group (placebo) will assume MAR. Imputed values in the BIIB104 treatment groups will be based on data from the placebo group using sequential regression MI model. Each sequential regression model (i.e., for imputation of values at a given week) will include visits of endpoint. This approach assumes no sustained benefit of BIIB104 after discontinuation of study treatment and limits post-discontinuation effects to that of placebo.

Two hundred imputations will be performed and from each of the imputed datasets, least square (LS) mean differences from placebo and their standard errors will be combined using Rubin's method [Rubin 1987]. PROC MIANALYZE procedure is used to produce a pooled LS mean estimate of treatment difference at Week 12, its 95% CI, and a pooled p-value.

Complementary Analysis: include data after intercurrent events

This is a complementary analysis to the primary and sensitivity analyses (efficacy estimand) for the ITT population. All observed data including those collected after intercurrent events [ICH E9 (R1) Addendum 2017], i.e. premature discontinuation of the study treatment, will be included. The estimate of this analysis reflects the treatment effect of BIIB104 seen as actually taken. This is considered [*de facto*] effectiveness estimand. When all data after intercurrent events are included, the same MMRM model as the primary analysis will be applied. In this complementary analysis, missing data are assumed to be missing at random [Rubin 1976].

The per-protocol analysis will be done using the same model as the primary analysis and applying in the per-protocol population.

Responder Analysis: threshold determined using distribution-based method

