This is a supplementary analysis to assess the effect of individual treatment response in the ITT population only. The threshold, defined as the minimal clinically important difference (MCID), will be estimated based on the distribution-based approach and will use 1/2 pooled standard deviation at baseline calculated from subjects in the ITT population. A subject will be classified as a responder if their change from baseline (in terms of improvement) is greater or equal to the threshold, otherwise they will be classified as a non-responder. All subjects with missing data at Week 12 will be classified as non-responders.

The number of responders and non-responders will be modelled using a logistic regression with treatment group and baseline included as covariates. Region will also be included but may be omitted in the case the model fails to converge.

Visit windows for mapping efficacy endpoints

For efficacy data that are summarized by visit, data collected on all scheduled visits and all unscheduled visits will be mapped to an appropriate analysis visit using the windowing scheme shown in the following few tables. If there are 2 or more assessments available in the same analysis window for a subject, the assessment closest to the target visit day will be used for analysis. If there are 2 or more assessments in the same analysis window with the same distance from the target visit day, the later assessment will be used.

Table 2: Visit Windows for Efficacy Endpoints: MCCB, [REDACTED], and PANSS

Analysis visit	Target visit day	Analysis visit window
Baseline	1	Prior to the time of, or within one day after, the first treatment dose
Week 2	15	[2, 28]
Week 6	43	[29, 70]
Week 12	85	[71, 91]

* If subject terminate the treatment before Day 71, their visits will be mapped to corresponding analysis visit based on the analysis day (ADY).

Table 3: Visit Windows for efficacy endpoints: UPSA-Bi, SCoRS, [REDACTED]

Analysis visit	Target visit day	Analysis visit window
Baseline	1	Prior to the time of, or within one day after, the first treatment dose
Week 12	85	[71, 91]
Early Termination	N/A	[2, 70]

* If subject terminate the treatment early before Day 71, their visits will be mapped to nominal visit of “early termination”.

Table 4: Visit Windows for Efficacy Endpoints: CGI-S/CGI-I

Analysis visit	Target visit day	Analysis visit window
Baseline	1	Prior to the time of, or within one day after, the first treatment dose
Week 6	43	[2, 70]
Week 12	85	[71, 91]

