* CGI-I does not have baseline collected and therefore its visits are applied to Week 6 and 12.

* If subject terminate the treatment early before Day 71, their visits will be mapped to corresponding analysis visit based on the analysis day (ADY).

Considerations for multiple comparison adjustments

There will be no multiple comparison adjustments for primary, secondary efficacy [REDACTED] endpoints, nor the subgroup analyses.

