4.4.3 Secondary Efficacy Endpoints

Three key secondary endpoints including changes from baseline to Week 12 in MCCB neurocognitive and overall composite scores, UPSA-Bi, and SCoRS will be applied by the primary analysis, sensitivity analysis, and complementary analysis described in [Section 4.4.1](#). A responder analysis for MCCB neurocognitive, UPSA-Bi Total score, and SCoRS Interviewer Rating Subtotal score only will also be applied as described in [Section 4.4.1](#).

Other secondary efficacy endpoints including MCCB individual domain (except working memory domain), PANSS total score, PANSS positive syndrome, PANSS negative syndrome, CGI-S will be applied by MMRM model of the primary analysis only, which is described in [Section 4.4.1](#).

The summaries of CGI-I at Week 12 will be displayed.

[figure not shown]

The analysis methods used for primary, secondary, [REDACTED] endpoints are listed in table 5:

Table 5: Analysis for Efficacy Endpoints:

Endpoints	Analysis	Analysis Population	Assumption for Missing Data
Primary endpoint and key secondary endpoints: MCCB Working Memory, MCCB Neurocognitive Composite, UPSA-Bi, SCoRS	Primary (for MCCB Working Memory, and Neurocognitive Composite): analysis of change from baseline to Week 12 (MMRM)	ITT and per-protocol population	Missing at Random (MAR)
	Primary (for UPSA-Bi and SCoRS): analysis of change from baseline to Week 12 (ANCOVA)	ITT and per-protocol population	N/A
	Sensitivity: multiple imputation using MCMC (MAR) for intermittent missing data; reference-based multiple imputation missing data post treatment discontinuation	ITT	Missing at Random (MAR) for intermittent missing data and Missing Not at Random (MNAR) for missing data post treatment discontinuation
	Complementary: include data after intercurrent events	ITT	Missing at Random (MAR)

	Responder (for MCCB Working Memory, Neurocognitive Composite, UPSA-Bi Total score, and SCoRS Interviewer Rating Subtotal score only): threshold determined using distribution-based method	ITT	N/A
Other secondary endpoints: MCCB individual domain (except working memory), MCCB overall composite score, PANSS total score, PANSS positive scale, PANSS negative scale, and CGI-S	Primary: analysis of change from baseline to Week 12 (MMRM)	ITT	Missing at Random (MAR)
[REDACTED]	[REDACTED]	[REDACTED]	[REDACTED]
[REDACTED]	[REDACTED]	[REDACTED]	[REDACTED]

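### SAP Table 3 (UPSA-Bi, SCoRS): the footnote on early treatment stop contradicts the table's own day windows and, applied as written, would remove off-drug Week 12 values from the complementary analysis

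*SAP*

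**What the plan says.** SAP 4.4.1, under the visit windows for efficacy endpoints, has three tables. Table 3 covers UPSA-Bi and SCoRS and has Baseline, Week 12 (target Day 85, Days 71-91) and Early Termination (Days 2-70). Its footnote reads: "If subject terminate the treatment early before Day 71, their visits will be mapped to nominal visit of" early termination.

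Table 2 (MCCB, PANSS) carries a footnote with the same trigger and a different destination: "If subject terminate the treatment before Day 71, their visits will be mapped to corresponding analysis visit based on the analysis day (ADY"). The Table 4 footnote (CGI-S, CGI-I) also maps by analysis day.

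Four other provisions bear on this:

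- Protocol 10.1: "All subjects who discontinue study treatment prematurely will be asked to remain in the study and continue all protocol-specified visits and procedures". Protocol Table 4 schedules UPSA-Bi and SCoRS only at Day 1 and at Week 12/ET.
- SAP 4.4.1, primary analysis: data are censored once study treatment is stopped early. For UPSA-Bi and SCoRS, "the primary analysis will be based on subjects who have both baseline and Week 12 assessments", by ANCOVA.
- SAP 4.4.1, complementary analysis: "All observed data including those collected after intercurrent events" are to be included, to estimate the effect of treatment as it was in fact taken. SAP 4.4.3 says that the key secondary endpoints, UPSA-Bi and SCoRS among them, "will be applied by the primary analysis, sensitivity analysis, and complementary analysis described in" Section 4.4.1.
- SAP 4.4.1, responder analysis: a subject without Week 12 data counts as a non-responder.

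**The concern.** The footnote depends on when treatment ended. The rows depend on when the assessment was made. The two agree for a subject who stops drug and leaves the study before Day 71. They disagree for a subject who stops drug before Day 71, stays in the study as Protocol 10.1 asks, and is tested between Days 71 and 91.

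That is the subject for whom the complementary analysis exists. MCCB has other post-baseline visits that can enter a repeated-measures model, but UPSA-Bi and SCoRS have one scheduled post-baseline assessment. If it loses its Week 12 label, the subject has no value for the endpoint. The complementary analysis would then add only those who stopped on or after Day 71. It would sit close to the on-treatment result while being described as a de facto effectiveness estimate.

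**Working it through.** **1. The plan's own figures.** The windowing rule rests on no stated number, but the group size is needed below. With a difference of 3.5, SD 7 and two-sided alpha 0.10 (Protocol 16.6), the normal approximation gives n = 2 × (1.645 + 0.842)² × (7/3.5)² = 49.5, so 50 per group. The noncentral t gives power of 79.9% at 50 and 80.6% at 51, so 51 is the t-test answer. Then 51/0.70 = 72.9, so 73 per group and 3 × 73 = 219. The plan's figures reproduce.

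**2. One record under each rule.** Drug is stopped on Day 50 and UPSA-Bi is done on Day 85.

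| Rule | Trigger | Result |
|---|---|---|
| Table 3 rows | Day of assessment | Week 12 |
| Table 3 footnote, as written | Treatment stopped before Day 71 | Early termination |
| Table 2 and 4 footnote wording | Treatment stopped before Day 71, then day of assessment | Week 12 |

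No text ranks the footnote against the rows. Stopping treatment cannot safely be read as leaving the study, because SAP 4.3.1 counts treatment discontinuation and study withdrawal separately.

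**3. Which analyses change if the footnote governs.**

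- MCCB Working Memory (primary endpoint): no change, since it uses Table 2.
- Primary ANCOVA for UPSA-Bi and SCoRS: no change, since values after the stop are censored anyway.
- Complementary analysis for UPSA-Bi and SCoRS: observed Week 12 values are lost. The sentence requiring a Week 12 assessment is written for the primary analysis, but the endpoint is the change to Week 12, so a value relabelled early termination cannot supply it.
- Responder analysis: possibly changed. The SAP does not say whether off-treatment values count there. If they do, an observed Day 85 result would be recorded as missing and so as non-response.

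**4. How many subjects.** Let s be the share stopping drug before Day 71 and r the share of those assessed on Days 71-91. The number affected per arm is 73 × s × r. The documents give neither s nor r, so both are assumed. The top value of s borrows the plan's 30% drop-out rate.

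| s | r = 0 | r = 25% | r = 50% | r = 100% |
|---|---|---|---|---|
| 10% | 0 | 1.8 | 3.7 | 7.3 |
| 20% | 0 | 3.7 | 7.3 | 14.6 |
| 30% | 0 | 5.5 | 11.0 | 21.9 |

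The range is 0 to about 22 per arm, or 0 to about 66 in the trial (3 × 21.9 = 65.7).

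**5. Illustration of the effect on the estimate.** Suppose also that subjects off drug keep no benefit. With them included, the complementary estimate is (1 − s)/(1 − s + s·r) of the on-drug effect. That is 0.8/0.9 = 0.89 at s = 20% and r = 50%, 0.70 at the extreme corner, and 1.00 when r = 0. With them left out, it stays at 1.00.

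**The case against.** The strongest reply is that the footnote merely explains the Early Termination row. Its Day 71 limit is that row's edge. Table 3 has no Week 2 or Week 6 row to receive an assessment made at an early exit, so it needs a separate label that Tables 2 and 4 do not, which would explain why the footnotes differ. Read with no limit at all, the footnote would also relabel the baseline visit, which nobody intends. The general rule maps scheduled and unscheduled visits by window, and the complementary analysis expressly takes in data after discontinuation.

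Much of this stands. A reader might infer from the footnote that every visit of such a subject is relabelled and that their Week 12 values can never reach the complementary analysis. The documents do not support that: the rows and the complementary-analysis text both point to inclusion. What remains is that the words state a different trigger, place no limit on visit day and depart from two parallel footnotes, so a programmer could fairly take Table 3 as a deliberate override.

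The size can also be challenged, rightly. Protocol 10.1 sets a minimum of safety checks, concomitant medications and unnamed key assessments for these visits, so UPSA-Bi and SCoRS are not guaranteed and r may be small. Reference-based imputation already provides one analysis of these endpoints that assumes no lasting benefit, though from imputed rather than observed off-drug values.

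**Conclusion.** The conflict is real and unresolved: the SAP gives two answers for the same UPSA-Bi or SCoRS record. Under one of them, an analysis that the SAP prescribes for these endpoints loses data it was designed to use. This deserves correction, but its reach is limited to the complementary analysis, and possibly the responder analysis, of two key secondary endpoints.

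The number affected could be zero. The range of 0 to about 22 per arm rests on the assumed s and r, and its upper end needs both at their maximum. A reader might also infer a definite degree of dilution. The documents do not support one: they give neither the number of retained discontinuers nor any residual effect off drug, and the 51 completers per group were derived for MCCB Working Memory. The fractions in step 5 show direction and scale only.

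**What to change.** Reword the Table 3 footnote so that it follows the rows, for example: *All post-baseline assessments are mapped by analysis day, Days 2-70 to Early Termination and Days 71-91 to Week 12, whether or not the subject is still on treatment.* Carry treatment status in a separate on/off-treatment flag. Off-treatment values are then censored in the primary analysis and kept in the complementary analysis. State in the responder paragraph whether off-treatment Week 12 values count.

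The cost is one footnote, one clarifying sentence and the matching programming. No new data are needed and the sample size does not change. It should be settled before unblinding, so that the choice is not made with results in view.

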4.4.2 Primary Efficacy Endpoint

4.4.2.1 Primary Analysis

The primary endpoint is the change from baseline in MCCB Working Memory Domain score to Week 12. The MMRM model will be applied to the primary endpoint and it is described in [Section 4.4.1](#). The same model will also be applied to per-protocol population.

4.4.2.2 Sensitivity Analysis

Reference-based multiple imputation approach will be performed on the primary endpoints using the methods as described in [Section 4.4.1](#).

4.4.2.3 Complementary Analysis

All observed data including those collected after intercurrent events will be applied by MMRM model to the primary endpoint.

4.4.2.4 Responder Analysis

The number of responders and response rate in MCCB Working Memory at Week 12 will be summarised and modelled using the methods as described in [Section 4.4.1](#).

4.4.3 Secondary Efficacy Endpoints

Three key secondary endpoints including changes from baseline to Week 12 in MCCB neurocognitive and overall composite scores, UPSA-Bi, and SCoRS will be applied by the primary analysis, sensitivity analysis, and complementary analysis described in [Section 4.4.1](#). A responder analysis for MCCB neurocognitive, UPSA-Bi Total score, and SCoRS Interviewer Rating Subtotal score only will also be applied as described in [Section 4.4.1](#).

Other secondary efficacy endpoints including MCCB individual domain (except working memory domain), PANSS total score, PANSS positive syndrome, PANSS negative syndrome, CGI-S will be applied by MMRM model of the primary analysis only, which is described in [Section 4.4.1](#).

The summaries of CGI-I at Week 12 will be displayed.

[figure not shown]

The analysis methods used for primary, secondary, [REDACTED] endpoints are listed in table 5:

Table 5: Analysis for Efficacy Endpoints:

Endpoints	Analysis	Analysis Population	Assumption for Missing Data
Primary endpoint and key secondary endpoints: MCCB Working Memory, MCCB Neurocognitive Composite, UPSA-Bi, SCoRS	Primary (for MCCB Working Memory, and Neurocognitive Composite): analysis of change from baseline to Week 12 (MMRM)	ITT and per-protocol population	Missing at Random (MAR)
	Primary (for UPSA-Bi and SCoRS): analysis of change from baseline to Week 12 (ANCOVA)	ITT and per-protocol population	N/A
	Sensitivity: multiple imputation using MCMC (MAR) for intermittent missing data; reference-based multiple imputation missing data post treatment discontinuation	ITT	Missing at Random (MAR) for intermittent missing data and Missing Not at Random (MNAR) for missing data post treatment discontinuation
	Complementary: include data after intercurrent events	ITT	Missing at Random (MAR)

	Responder (for MCCB Working Memory, Neurocognitive Composite, UPSA-Bi Total score, and SCoRS Interviewer Rating Subtotal score only): threshold determined using distribution-based method	ITT	N/A
Other secondary endpoints: MCCB individual domain (except working memory), MCCB overall composite score, PANSS total score, PANSS positive scale, PANSS negative scale, and CGI-S	Primary: analysis of change from baseline to Week 12 (MMRM)	ITT	Missing at Random (MAR)
[REDACTED]	[REDACTED]	[REDACTED]	[REDACTED]
[REDACTED]	[REDACTED]	[REDACTED]	[REDACTED]

4.5 Safety Analysis

4.5.1 General considerations

Analysis population

Safety population will be used for safety analyses of adverse events, clinical laboratory data, Columbia Suicide Severity Rating Scale (C-SSRS) data, ECG data and vital signs data.

Safety treatment groups

Different from efficacy analysis, for safety treatment group if a subject who was randomized to a placebo group accidentally received one or more doses of the active treatment during the study, he or she will be classed to low or high dose group based on the dose group of the active treatment received. A listing of these subjects will be provided. Safety treatment groups will be the same as the randomization treatment groups for other subjects (subjects randomized to active treatment groups, and subjects randomized to placebo without any accidental active dose). Safety treatment groups will be used for all the safety analyses unless otherwise specified.

Incidence and incidence proportion

Incidence and incidence proportion will be provided in incidence tables. Incidence is defined as the number of subjects who experienced an event. Incidence proportion is defined as the number of subjects who experienced an event divided by total number of subjects in the analysis population, i.e., percentage. Each subject will be counted only once within each category.

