12.1. BIIB104 Study Treatment

BIIB104 and its matched placebo will be provided as capsules (Size 1) for oral administration. The BIIB104 0.15 mg and 0.5 mg capsules and their matched placebos will be supplied in separate blister cards and labeled in accordance with all applicable regulatory requirements. At a minimum, the label will include a study reference code, study treatment identifier, quantity of dosage units, lot number, and other pertinent information in accordance with local law. The expiry or use-by date is stored in the IRT system, and printable assignment reports are available to site staff. Study treatment should not be used after the expiration, expiry, or use-by date.

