4.1.1 Analysis Population

- Intent-to-treat (ITT) population:

The ITT population is defined as all randomized subjects who received at least one dose of study treatment (BIIB104 or placebo). Subjects will be in the treatment group to which they were randomized in statistical analyses based on the ITT population.

- Per-protocol (PP) population:

The PP population is defined as all subjects in the ITT population who do not have major protocol deviation(s) that impact efficacy. Exclusion of subjects from the PP population will be determined by the SMT members including but not limited to medical director, clinical pharmacologist and biostatistician. The main reasons for exclusion will be documented.

- Safety population:

The safety population is defined as all randomized subjects who received at least 1 dose of study treatment (BIIB104 or placebo). Subjects will be in the treatment group they received in statistical analyses based on the safety population.

- [REDACTED]

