4.3.5 Study Drug Exposure and Study Drug Compliance

A summary table of study drug exposure and compliance will be provided. Number of weeks on study treatment (BIIB104 or placebo), will be calculated as (date of last dose – date of first dose +1) /7. The cumulative duration of weeks on study treatment will be displayed (≥ 1 , ≥ 2 , ≥ 4 , ≥ 6 , ≥ 8 , ≥ 12 weeks). Descriptive statistics will be presented for days on study treatment.

Compliance, which is the percentage of study treatment taken up to the last dose, calculated as (the actual number of dose taken / by the number of doses a subject is expected to take until the date of last dose) *100, will be summarized both as a continuous variable and a categorical variable (i.e., < 80, 80 to < 90, 90 to ≤ 100 , and $> 100\%$).

Time on study (in weeks) will be summarized both as a continuous variable and a categorical variable. The categorical variable will be grouped as ≤ 2 , $2 - \leq 4$, $4 - \leq 6$, $6 - \leq 8$, $8 - \leq 10$, $10 - \leq 12$, and > 12 weeks.

A listing of study drug administration records for placebo subjects who received any dose of active treatment will be provided.

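### SAP 4.5.1 keeps every active-arm subject in the randomized dose group for safety, whatever was taken, which contradicts the as-received rule in SAP 4.1.1

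*SAP*

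**What the plan says.** SAP 4.1.1 (Analysis Population) gives the general rule for safety, without exception: "Subjects will be in the treatment group they received in statistical analyses based on the safety population".

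SAP 4.5.1 (General considerations, safety treatment groups) gives the working rule. Its trigger is "if a subject who was randomized to a placebo group accidentally received one or more doses of the active treatment during the study"; in that case "he or she will be classed to low or high dose group based on the dose group of the active treatment received". For the rest, "Safety treatment groups will be the same as the randomization treatment groups for other subjects", and the SAP spells out who these are: "subjects randomized to active treatment groups, and subjects randomized to placebo without any accidental active dose". The scope is broad: "Safety treatment groups will be used for all the safety analyses unless otherwise specified". No other safety section in the available text specifies otherwise.

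Two listings deal with wrong treatment. SAP 4.5.1 promises one of the reassigned placebo subjects, and SAP 4.3.5 adds another: "A listing of study drug administration records for placebo subjects who received any dose of active treatment will be provided". Neither covers subjects randomized to an active dose.

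Protocol 16.4.1 defines the safety population but gives no grouping rule, so it does not settle which SAP section governs.

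**The concern.** The two SAP sections give different answers for the same subject. An analyst who follows 4.5.1 counts a 0.15 mg subject who actually took 0.5 mg as low dose; one who follows 4.1.1 counts the same subject as high dose. Because 4.5.1 names the active arms among those kept as randomized, it cannot be read simply as a fuller statement of 4.1.1. For those arms it replaces the as-received principle.

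Safety and tolerability is a secondary objective, and the safety tables compare two doses with placebo. An event placed under the wrong dose blurs that comparison. The error is also hard to see, since an active-arm subject given the wrong treatment is outside both listings meant to show such cases.

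The situation is physically possible: according to Protocol 12.1, the two strengths of "capsules and their matched placebos will be supplied in separate blister cards and labeled in accordance with all applicable regulatory requirements". If the conflict is found only after unblinding, the choice between the two rules would be made with the affected events in view.

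**Working it through.** The main check is a comparison of texts. The plan has no figure of its own to reproduce on this point.

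**Step 1: apply both rules to each kind of error.**

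| Randomized to | Actually took | Group under 4.1.1 | Group under 4.5.1 | In a wrong-treatment listing? |
|---|---|---|---|---|
| Placebo | one active dose level throughout | dose taken | dose taken | yes |
| 0.15 mg | 0.5 mg throughout | 0.5 mg | 0.15 mg | no |
| 0.5 mg | 0.15 mg throughout | 0.15 mg | 0.5 mg | no |
| Either active dose | placebo only | placebo | randomized active dose | no |
| Either active dose | a mixture | not defined | randomized active dose | no |
| Placebo | both active strengths | not defined | not defined | yes |

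Rows 2 to 4 are direct contradictions. Rows 5 and 6 show that 4.1.1 does not define what counts as received under mixed exposure, and that 4.5.1 leaves the last case open.

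**Step 2: size per subject.** Inputs: 73 subjects per arm (Protocol 16.6; I assume all are dosed) and incidence as subjects with an event divided by subjects in the group (SAP 4.5.1). Take one subject randomized to 0.15 mg who took 0.5 mg and had the only event.

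- Under 4.5.1: low dose 1/73 = 1.37%, high dose 0/73 = 0%.
- As received: low dose 0/72 = 0%, high dose 1/74 = 1.35%.
- BIIB104 total: 1/146 = 0.68% either way.

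If an active-arm subject received only placebo, the total does change. Under 4.5.1 it is 1/146 = 0.68% with placebo at 0/73. As received it is 0/145, with placebo at 1/74 = 1.35%.

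**Step 3: the 5% cut-offs.** SAP 4.5.2.1 plans one table of terms at 5% or more in any group, and one of terms at least 5% higher than placebo in either dose (read here as percentage points). The count needed is 0.05 × 72 = 3.60, 0.05 × 73 = 3.65 or 0.05 × 74 = 3.70, so four subjects in each case. One subject can decide it. In both examples below, one low-dose subject with the event actually took 0.5 mg, and placebo has 0/73.

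- Three low-dose and three high-dose subjects as randomized: 3/73 = 4.11% in each arm, so the term is in neither table. As received: 2/72 = 2.78% and 4/74 = 5.41%, so the term enters both, because of the high dose.
- Four low-dose and three high-dose subjects as randomized: 4/73 = 5.48% and 3/73 = 4.11%. As received: 3/72 = 4.17% and 4/74 = 5.41%. The term stays in both tables, but the dose above 5% switches from low to high.

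**The case against.** The best reply is that the contradiction is narrow. It is clear-cut only for a subject on the wrong treatment throughout. Drug is dispensed at seven visits (Protocol Table 4) by container number through the IRT (Protocol 12.1.1), so a single error would more likely give mixed exposure. There 4.1.1 is silent, and 4.5.1 could be seen as filling the gap. This limits how often the sections collide, but it does not rescue the rule: 4.5.1 fills the gap for active arms by ignoring what was received.

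Second, part of the audit trail exists. A 0.15 mg subject who takes 0.5 mg has exceeded the assigned dose, which calls for an Overdose form and dosing entries (Protocol 15.4.2). Protocol deviations are listed too (SAP 4.3.4). This stands, but an error in the downward direction is not an overdose, and none of these records changes the column in which events are counted.

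Third, the documents give no rate of such errors. That is right, and it bounds the point.

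A reader might go further in three ways that the documents do not support.

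- *That one misplaced seizure would change the safety conclusion for a dose.* Suspected seizures go to an independent neurologist panel and then to the IDMC, and the stopping criterion asks only whether the subject was on active treatment (Protocol 7.3). Seizures are also reported as SAEs (Protocol 15.3.2) and listed separately (SAP 4.5.2.1).
- *That moving a placebo subject to an active group after one active capsule is a mistake.* It is an explicit, deliberate rule that keeps drug-exposed subjects out of the comparator.
- *That events should follow the treatment taken at onset.* SAP 4.5.1 defines incidence over subjects in a group. Splitting a subject's events across columns would need a new denominator rule.

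**Conclusion.** The point holds. For subjects randomized to an active dose, SAP 4.5.1 contradicts SAP 4.1.1, and no other section resolves it. Followed as written, 4.5.1 counts a wrongly dosed active-arm subject in the wrong column and leaves that subject out of both wrong-treatment listings. This is a rule that gives the wrong answer, not merely a missing detail.

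The size is about 1.4 percentage points per affected subject with an event, assuming 73 dosed per arm. That is enough to change what the 5% tables show when a count is at the margin. The effect depends entirely on dosing errors occurring. If there are none, no table changes. For errors between the two active doses, the BIIB104 total column is also unaffected. The conclusion does not rest on any claim about seizures, on the placebo rule being wrong, or on timing of events relative to an error. It is worth correcting because the correction is cheap and must be made blind to be credible.

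**What to change.** Before unblinding, make SAP 4.1.1 and 4.5.1 state the same as-received rule for all three arms, assigning each subject to exactly one safety group and covering mixed exposure. One workable form is the highest active dose actually taken after randomization, with placebo for subjects who took none. This keeps the existing placebo rule, extends it to the active arms, settles the placebo subject who took both strengths, and fits the one-subject, one-denominator definition of incidence. Another single-group rule would serve, provided it is fixed in advance.

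Replace the placebo-only listings in SAP 4.3.5 and 4.5.1 with one listing of every subject who received any treatment other than the one assigned, showing what was taken and when. Restrict it to doses after randomization, since all subjects take placebo in the lead-in.

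The cost is a revised paragraph in 4.5.1, a matching sentence in 4.1.1, and a wider selection criterion for one listing. It needs no new data collection: dosing information is already recorded on the dosing CRF (Protocol 15.4.2).
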